## **10.5 Vital Signs**

Vital sign measurements (blood pressure, heart rate, temperature [Visit 1 only]), height (Screening Visit only), and weight will be provided in a data listing by subject.

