## 6.2 Summary of Nonclinical Studies

Nonclinical studies necessary to support clinical studies have been performed and are summarized below. Further information can be obtained from the Investigator Brochure (IB).

ASN002 showed potent inhibition of SYK and JAK kinases in biochemical assays with an IC50 range of 5-46 nM. In mechanistic cell-based studies involving IL-6 and IgE stimulation, ASN002 strongly blocks the SYK and JAK family kinase signaling pathways. The compound inhibited the proliferation of a broad range of lymphoma and solid tumor cell lines including H929, Pfeiffer, SUDHL6 and OCI-Ly10. In a multiple myeloma model (H929), ASN002 exhibited significant efficacy in inhibiting tumor growth (>95% at 90 mg/kg dose). It also delayed the onset of hind limb paralysis in the human erythroleukemia (HEL) model by nearly 33%, compared to vehicle.

ASN002 exhibits a medium to rapid rate of oral absorption, moderate to good oral bioavailability and short T1/2 in pre-clinical species. It exhibits good permeability characteristics and does not

appear to be a Pgp substrate in vitro. It is moderately bound to plasma protein and exhibits good metabolic stability in vitro. Limited metabolism may occur via 2C8, 2D6 and 3A4 pathways. Glucuronidation does not appear to be a pathway for metabolism of ASN002. ASN002 does not appear to have significant inhibitory activity on any of the CYP450 isozymes evaluated, which suggest a low potential for drug-drug interactions. Adequate systemic exposure was observed at the NOAEL in the 28-day GLP toxicology studies in both rat and dog.

The results of the mutagenicity studies suggest the genotoxic potential of ASN002 would be low. Safety pharmacology studies suggest no adverse effects on the cardiovascular (CV), CNS or respiratory systems. Decreased systolic, mean, and pulse blood pressure were observed in the dog, but the effects were reversible and can be easily monitored in the clinic.

In both the rat and dog 28-day toxicity studies, NOAELs were demonstrated. The primary toxicities in bone marrow and lymphoid tissue and were reversible. In dogs, the bile duct and gall bladder were additional target organs. One would expect hematologic changes before significant toxicity in the bile duct or gall bladder.

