#### 15.5.5 Vital Signs

Descriptive statistics for vital signs (e.g., systolic and diastolic blood pressure, pulse rate, temperature, and body weight) and their changes from baseline at each visit and at the end of study will be presented by dose level.

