#### 15.5.7 Electrocardiogram

Descriptive statistics for ECG parameters (e.g., heart rate, PR interval, QRS interval, QT interval, and QTc interval) at baseline and changes from baseline at each assessment time point will be presented by dose level. QTc interval will be calculated using both Bazett [ $QTcB = QT/(RR)^{1/2}$ ] and Fridericia [ $QTcF = QT/(RR)^{1/3}$ ] corrections; and if RR is not available, it will be replaced with 60/HR in the correction formula.

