## **10.7 Electrocardiograms**

For QTcF intervals, the proportion of QTcF above the upper limit of normal – both  $\geq 450$  msec and  $\geq 481$  msec will be considered as upper limits of normal QTcF – and change from baseline  $> 30$  msec and  $> 60$  msec will be presented. Denominators for percentages will be the number of subjects in the analysis population for the treatment cohort summarized.

ECG data will be displayed in a data listing by subject.

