### **14 SUMMARY OF CHANGES FROM THE PROTOCOL**

No changes from the protocol were made in this analysis plan.

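### SAP 10.5 and 10.7 omit the by-dose vital-sign and ECG change-from-baseline summaries that Protocol 15.5.5 and 15.5.7 promise, and SAP 14 wrongly says nothing changed

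*SAP*

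**What the plan says.** **Protocol.** Section 15.5.5 promises descriptive statistics for blood pressure, pulse, temperature and weight, "and their changes from baseline at each visit and at the end of study will be presented by dose level". Section 15.5.7 does the same for ECG: "Descriptive statistics for ECG parameters (e.g., heart rate, PR interval, QRS interval, QT interval, and QTc interval" are to be given "at baseline and changes from baseline at each assessment time point will be presented by dose level". It adds that "QTc interval will be calculated using both Bazett" and Fridericia corrections. The synopsis agrees in outline: vital signs and ECG findings are to be summarised by dose level and time point, as descriptive statistics or frequency distributions.

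**SAP.** Section 10.5 sends blood pressure, heart rate, temperature, height and weight to a listing: "height (Screening Visit only), and weight will be provided in a data listing by subject". Section 10.7 presents the proportion with QTcF at or above 450 and 481 msec, and the proportion with QTcF change above 30 and above 60 msec. Everything else falls under "ECG data will be displayed in a data listing by subject". Section 14 states: "No changes from the protocol were made in this analysis plan".

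**Precedence.** The opening of Protocol Section 15 gives the SAP priority where the two documents differ.

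**The concern.** Safety and tolerability are the primary objective of Part A and part of the primary objective of Part B. SAP 2.3.2 names vital signs and the 12-lead ECG among the evaluations used to define tolerability. A programmer working from the SAP would produce no table of observed values or changes for any post-baseline vital sign, and no table of continuous values for any ECG parameter. A reader of the report who wanted to know whether blood pressure or the PR interval moved with dose would have to work it out from individual listings.

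The departure is also undeclared. A reader who relies on SAP 14 would believe that the protocol's safety tables are still planned.

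**Working it through.** There is no plan figure to reproduce; the check is a comparison of texts, with a count of the scheduled measurements.

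**1. Promised and specified outputs**

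| Item | Protocol 15.5.5 / 15.5.7 | SAP 10.5 / 10.7 |
|---|---|---|
| Blood pressure, pulse | Descriptive statistics and change, each visit and end of study, by dose | Listing only |
| Weight | Same | Listing; screening value summarised under SAP 8.5 |
| Temperature | Same | Listing, Visit 1 only |
| Heart rate (ECG), PR, QRS, QT | Descriptive statistics and change, each time point, by dose | Listing only |
| QTc, Fridericia | Same | Two threshold and two change categories, no time point stated; listing |
| QTc, Bazett | Same | No summary |

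The only change-from-baseline summary left in either domain is the pair of QTcF change categories.

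**2. Could another SAP section supply the tables?** SAP 6.6 defines what descriptive statistics means but adds no output. SAP 7.3 fixes the pre-dose Day 1 assessment as baseline for ECG and vital signs, yet no vital-sign table uses it. SAP 10.4 keeps absolute and change-from-baseline summaries for laboratory data, so the reduction is specific to these two domains. The fallback to listings if Part B is not completed (SAP 2.3.1.1 and 9) concerns efficacy only.

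**3. Which text governs?** The SAP, by Protocol Section 15. The protocol wording therefore does not bring the tables back.

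**4. How much data is involved?** From Protocol Table 3 (Part A), vital signs in a twice-daily cohort are scheduled as follows:

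- Day 1: predose, 1, 2, 4 and 12 h = 5
- Day 2, Day 8 and Day 22: 1 each = 3
- Day 15: predose, 1, 2, 4 and 12 h = 5
- Cycle 2 Day 1: 1

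The total is 5 + 3 + 5 + 1 = 14, of which 14 − 1 = 13 follow the baseline. Once-daily cohorts add Day 3 and Day 16, giving 16 in total and 15 after baseline. ECGs follow the same pattern without Cycle 2 Day 1: 12 after baseline (twice daily) or 14 (once daily). Part A plans approximately 64 subjects, spread over many dose cohorts. Part B plans 6 × 14 = 84 subjects starting at one dose, on the sparser Table 2 schedule.

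**5. Does any decision use the missing tables?** Protocol 8.5.1 gives the safety review committee vital signs and ECG findings after each cohort, and SAP 11.1 repeats that committee's role. The MTD rests on DLT counts (Protocol 8.5.2, SAP 2.3.2). Neither uses the end-of-study tables.

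**The case against.** The strongest reply is that little is lost in practice.

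- SAP 6.6 sorts listings by study part, dosing cohort, subject and time, so each cohort's serial values appear together. With 3 to 6 subjects per Part A dose level they can be read directly, and a mean of so few is imprecise.
- Investigators review vital signs and ECGs for clinical significance (Protocol 12.8 and 12.9). Findings that count as adverse events are tabulated by cohort under SAP 10.1.
- QTcF change survives as categories, and the synopsis permits frequency distributions.
- The protocol lets the SAP govern, so fewer tables is a permitted choice.

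Most of this stands, and it limits the consequence. It does not remove the mismatch. Sections 15.5.5 and 15.5.7 are more specific than the synopsis, and vital signs receive neither form of summary. The protocol chose descriptive tables knowing its cohort sizes, and the small-cohort argument is weaker for Part B's 84 subjects. A permitted reduction still has to be declared.

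A reader might infer more than the documents support:

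- **That a dose-related change could not be detected at all.** The sorted listings and the adverse event tables contradict this.
- **That dose selection or subject protection is weakened.** The committee sees these data as the study proceeds.
- **That the protocol treats blood pressure as a flagged human risk.** Protocol 6.2 does say "Decreased systolic, mean, and pulse blood pressure were observed in the dog", but the sentence before it reports that safety pharmacology suggested no adverse cardiovascular effects. The rest of the same sentence calls the changes reversible and easy to monitor. That describes feasibility; it is not a commitment to tabulate.
- **That nothing is summarised.** Screening weight and height are (SAP 8.5), and QTcF categories are.

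**Conclusion.** The point holds as a discrepancy between protocol and SAP with a limited consequence. Under the governing SAP, no post-baseline vital sign and no continuous ECG parameter would be summarised by dose, Bazett QTc would have no summary, and the statement in SAP 14 is incorrect.

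The loss is the by-dose summary, in the final safety report, of shifts that investigators did not record as adverse events. Escalation, the MTD and the reporting of clinically significant findings are unaffected. It is worth correcting because it bears on a primary safety objective and costs little.

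This rests on reading SAP 10.5 and 10.7 as the full list of planned outputs for these domains; no other SAP section adds to them. The documents do not say whether the reduction was intended, and the conclusion does not depend on that.

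**What to change.** 1. In SAP 10.5, add observed value and change from baseline by visit or time point and by cohort for blood pressure, pulse and weight, using the SAP 7.3 baseline.
2. In SAP 10.7, add the same for heart rate, PR, QRS, QT and QTc (Bazett and Fridericia). Keep the QTcF category table.
3. Correct SAP 14. If any reduction is kept, for example dropping Bazett, declare it there and justify it.
4. Before adding a temperature change table, reconcile when temperature is collected. Footnote d of Protocol Table 1 includes it in vital signs at every listed visit. Protocol 12.8 limits it to Visit 1 unless clinically indicated, and SAP 10.5 to Visit 1. Restoring Protocol 15.5.5 unchanged would carry that conflict into the SAP.

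The cost is a few standard tables from measurements already scheduled, with no new data collection. The downside is that Part A means, from 3 to 6 subjects per dose level, will be imprecise and should be read with the listings.

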## **10.6 Pregnancy Test**

Serum or urine pregnancy testing is required at screening and within 72 hours of Day 1 of every Cycle for females of childbearing potential. Results of pregnancy tests will be provided in a data listing by subject.

## **10.7 Electrocardiograms**

For QTcF intervals, the proportion of QTcF above the upper limit of normal – both  $\geq 450$  msec and  $\geq 481$  msec will be considered as upper limits of normal QTcF – and change from baseline  $> 30$  msec and  $> 60$  msec will be presented. Denominators for percentages will be the number of subjects in the analysis population for the treatment cohort summarized.

ECG data will be displayed in a data listing by subject.

## **10.8 Physical Examinations**

A complete physical examination (PE) will be performed at the Screening and End of Treatment visits. The examination will include an assessment of the following: general appearance, skin, head and neck (including eyes, ears and throat), thorax, lymph nodes, thyroid, musculoskeletal/extremities (including spine), cardiovascular, lungs, abdomen and neurological systems. The screening exam will also include a measurement of body height and weight. The investigator will review all PE findings for clinical significance. Findings from the screening PE will be recorded as Medical History. Except for the screening PE, only changes from the previous PE will be recorded. Clinically significant changes from the screening PE will be captured as AEs, and analyzed according to the criteria in [Section 10.1](#).

A data listing, comprised of status of whether or not each assessment was conducted and date of each assessment, for physical examinations will be presented by subject.

# **11 OTHER ANALYSES**

## **11.1 Dose Escalation Safety Analyses**

The study will include multiple safety analyses for the dose escalation component (Part A). Each treatment cohort is viewed as a separate safety analysis, insofar as the safety review committee will decide whether the dose escalation will continue to the next planned (or intermediate) dose level, if additional subjects will be added to the current dose level, or if the dose escalation will be stopped. The safety review committee can also terminate the study due to safety concerns. Each review will be conducted with the latest available data.

---

A data listing of dose-limiting toxicities (DLTs) for Part A will be presented by subject.

### **11.2 Pharmacokinetic and Pharmacodynamic Analysis**

Pharmacokinetic (PK) analysis will be included in a separate analysis plan.

Part A and Part B may be combined for population PK/PD analysis. This analysis will be included in a separate population PK/PD analysis plan.

### **12 INTERIM ANALYSIS**

An interim analysis is not applicable to this study. As this is an open-label study, appropriate analyses will be conducted on an ongoing basis.

### **13 END-OF-STUDY-ANALYSIS**

A final analysis will be conducted after the last patient completes or discontinues the study and the resulting clinical database has been cleaned, quality checked, and locked.

### **14 SUMMARY OF CHANGES FROM THE PROTOCOL**

No changes from the protocol were made in this analysis plan.

